### **5.5.4. Blood Product Usage**

Blood product usage will be summarized for the following:

- Number of participants receiving 1 or more RBC transfusions from start of the andexanet bolus through 12 hours after the end of surgery
- Mean number of RBC units (treated as a continuous variable) transfused per participant from the start of the andexanet bolus through 12 hours after the end of surgery
- Number of participants receiving non-RBC, non-platelet blood products and/or hemostatic agents (both systemic and topical) through 12 hours after the end of surgery

For each of these blood product usage variables, descriptive statistics and CIs will be provided.

### **5.5.5. Intraoperative Blood Loss**

The volume of blood loss (mL) – predicted, actual, and actual minus predicted – will be summarized with descriptive statistics and CIs.

### **5.5.6. Transfusion-Corrected Change in Hemoglobin**

Baseline and change from baseline to nadir (within 12 hours after the end of surgery) in transfusion-corrected (ie, on only those participants having received whole blood or packed RBCs during surgery) hemoglobin (mg/dL) will be summarized with descriptive statistics and CIs.

### **5.5.7. Healthcare Encounter and Surgical Intervention**

Healthcare encounter will be summarized for the following:

- Time from signing of informed consent to start of surgery (hours)
- Time from clinical presentation to start of surgery (hours)
- Duration of index hospitalization (hours)

- Time hospitalized in a PACU (hours)
- Time hospitalized in an ICU (hours)
- Length of surgery (hours)
- Total time in OR (hours)
- Occurrence of re-hospitalization within 30 days of enrollment (yes/no)
- Length of re-hospitalization (days) through 30 days post enrollment, as the aggregate number of days spent re-hospitalized

For each of these healthcare encounter variables, descriptive statistics and CIs will be provided.

### **5.5.8. Post-Surgical Major Bleeding**

Post-surgical major bleeding will be summarized for the following:

- Occurrence of post-surgical bleeding (yes/no), as defined by ISTH criteria ([Schulman, 2010](#); Section 7) within 12 hours after the start of the initial surgery
- Occurrence (yes/no) of re-operations for bleeding (including for surgical wound hematomas) within 12 hours after the end of the initial surgery

For each of these post-surgical major bleeding events, descriptive statistics and CIs will be provided.

### **5.5.9. Tissue Factor Pathway Inhibitor (TFPI)**

The TFPI activity will be measured using plasma samples in a Central Laboratory using a validated assay. The TFPI functional activity will be determined using a commercial kit. The assay measures FXa chromogenic activity following FX activation by factor VIIa/TF added to the plasma. The TFPI activity is quantified by using a TFPI standard with U/mL as the readout. Binding of andexanet to TFPI will reduce the TFPI activity readout.

Baseline and change from baseline in TFPI activity (U/mL) post administration of andexanet will be summarized with descriptive statistics and CIs at each applicable time point/visit.

### **5.5.10. Anti-IIa Activity**

Anti-IIa activity levels will be measured in patients taking enoxaparin using plasma samples. Anti-IIa activity will be measured using a modified chromogenic assay. Anti-IIa activity results will be performed in a Central Laboratory.

Baseline and change from baseline in anti-IIa activity (IU/mL) will be summarized, for participants on enoxaparin only, with descriptive statistics and CIs at each applicable time point/visit.

## **5.6. Safety Analyses**

Safety will be assessed by examining the following endpoints and analyzed using the Safety Set:

- Adverse events (AEs) (including serious adverse events [SAEs]), vital signs, and clinical laboratory measurements

- TEs within 30 days of enrollment, including those suspected and confirmed by adjudication
- Centrally-adjudicated deaths within 30 days of enrollment, including all-cause mortality and cardiovascular mortality
- Antibodies to FX, FXa, and andexanet

### 5.6.1. Extent of Exposure

Participant compliance with the assigned treatment will not be evaluated since all procedures are performed in the hospital by trained professionals. Treatment modification with corresponding modification type will be tabulated along with descriptive statistics on the length of bolus and infusion duration; these results will be summarized by the dose of andexanet received (low, high, Total). Results will be presented for overall and by prior FXa inhibitor for the Safety Set.

### 5.6.2. Adverse Events

Adverse events are defined in Protocol Section 9.1.1 and Section 6.1 of this statistical analysis plan.

AEs will be coded according to the Medical Dictionary for Regulatory Activities (MedDRA) dictionary version 23.0 or later. In the analysis of treatment-emergent adverse events (TEAEs), all events recorded as occurring before first study treatment will be considered baseline conditions. Related TEAEs are events considered related to study treatment by the Investigator.

The number of events and the number of participants who experienced at least one TEAE reported through the Day 30 Follow-up Visit will be presented. TEAEs that are considered by the Investigator to be related to either the study medication or usual care, TEAEs that lead to early withdrawals, and SAEs will be summarized in the same manner.

#### 5.6.2.1. Overall Summary of Adverse Events

An overall summary of TEAEs and SAEs will be presented. The number of events (E) and number of participants with events (n, %) will be shown for the following:

**Table 3: Treatment-Emergent Adverse Events (TEAEs) and Serious AEs**

Events
Any Adverse Event
Adverse Events Leading to Withdrawal of Study Drug
Adverse Events by Relationship (Related, Not Related)
Adverse Events by Severity (Mild, Moderate, Severe)
Adverse Events of Special Interest (Arterial Systemic Embolism, Deep Vein Thrombosis, Myocardial Infarction, Pulmonary Embolism, Ischemic Stroke, Transient Ischemic Attack)

These tabulations will be prepared separately for all TEAEs and SAEs. Additionally, the number and percentage of participants who died on study will be presented.

#### 5.6.2.2. TEAEs and SAEs by System Organ Class (SOC) and Preferred Term

The number and percentage of TEAEs will be presented by SOC and Preferred Term. At the participant level, participants are counted once in each SOC and Preferred Term. Percentages

will be based on the total number of treated participants. SOC's will be listed in alphabetical order, and Preferred Terms within each SOC will be sorted by descending frequency of participants reporting the event.

SAEs, TEAEs leading to withdrawal of study drug, and TEAEs occurring in  $\geq 5\%$  of patients will be tabulated by SOC and Preferred Terms in a similar manner.

Additional tables summarizing TEAEs by surgery type and baseline FXa inhibitor may also be provided.

TEAEs and treatment-emergent related adverse events will also be tabulated but at the Preferred Term level only, for number of participants as well as for number of events, with Preferred Terms sorted by descending frequency.

Participants with events during the screening period (Pre-treatment adverse events [PTAEs]) will be presented in a data listing.

#### **5.6.2.3. AEs and SAEs by SOC, Preferred Term, and Relationship**

The number of TEAEs and the number and percentage of participants with events will be presented by SOC and Preferred Terms for all relationship levels (related, not related); if a participant has multiple events at the same relationship status for a particular SOC or Preferred Term, he/she is counted only once for that SOC or Preferred Term but all occurrences are counted at the event level. SAEs will be summarized similarly.

#### **5.6.2.4. AEs and SAEs by SOC, Preferred Term, and Severity**

The number and percentage of participants with events will be presented by SOC and Preferred Term as described above, by worst severity (mild, moderate, severe). If a participant has more than one occurrence of a TEAE, the most severe occurrence will be summarized for each participant per SOC/Preferred Term.

#### **5.6.2.5. Deaths, Other SAEs, and Other Significant Adverse Events**

The number and percentage of participants with adverse events leading to death will be presented by SOC and Preferred Term as described above. Additionally, those events leading to death which were COVID-19 related will also be tabulated in a similar fashion.

Furthermore, participants will have their survival status reported by phone on the Day 30 or End of Study visit. This assessment will record the participant's status as alive or provide the date, time, and cause of death. All deaths will be assessed by the EAC. Deaths will be classified by the following:

- Cardiovascular causes (ie, resulting from myocardial infarction [MI], sudden cardiac death, heart failure, stroke, cardiovascular procedures, cardiovascular hemorrhage, and other cardiovascular causes)
- Non-cardiovascular causes

All participants who died up through the 30-Day Follow-up Visit will be tabulated by reason for death (Cardiovascular, non-cardiovascular). In addition, 95% CIs for the proportions will be reported.

#### **5.6.2.6. Adverse Events of Special Interest (AESIs)**

Participants will be monitored carefully for signs and symptoms of TEs (version 23.0 or later computed tomography [CT]/magnetic resonance imaging [MRI], electrocardiogram [ECG]/cardiac enzymes, lower extremity ultrasound, pulmonary vascular imaging). Investigators are requested to consult the guidance listed in the protocol when considering whether an event should be considered a TE and therefore, be submitted for adjudication. All events submitted for adjudication will be formally considered a suspected TE. Both suspected TEs and TEs confirmed by adjudication will be monitored as safety endpoints.

All TEs up to the last study visit (ie, Day 30) will be assessed by the EAC and summarized descriptively, including whether (and to what extent) participants were re-anticoagulated prior to the thrombotic event up to the last study visit (ie, Day 30).

The Investigator will determine whether a TE is attributable to andexanet, while the DSMB will determine whether the occurrence of TEs in aggregate (related or not) warrant changes to the study. Detailed definitions of thrombotic events (including arterial systemic embolism, deep vein thrombosis, myocardial infarction, pulmonary embolism, ischemic stroke, and transient ischemic attack) will be provided in the EAC Charter as well as in the protocol.

The following tabulation of TEs will be performed:

- Incidence of suspected TEs, by detailed adverse event of special interest (AESI) term (arterial systemic embolisms, cerebrovascular accident or stroke, deep vein thromboses, myocardial infarction, pulmonary embolisms, transient ischemic attacks)
- Incidence of TEs confirmed by adjudication, by detailed AESI term (arterial systemic embolisms, cerebrovascular accident or stroke, deep vein thromboses, myocardial infarction, pulmonary embolisms, transient ischemic attacks)

#### **5.6.3. Analyses for Laboratory Tests**

In general, only laboratory value collected at scheduled visit/time points will be summarized. Laboratory value collected at unscheduled visits will be presented in data listings only. If an assessment is repeated for a given scheduled visit/time point, the last value will be used for summary purposes, but all values will be presented in data listings.

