  - h. Transfusion corrected change in hemoglobin from baseline to nadir within 12 hours after the end of surgery
  - i. Time from the signing of informed consent to the start of surgery
  - j. Time from clinical presentation at treatment facility to the start of surgery
  - k. Length of index hospitalization, assessed at the Day 30 Visit
  - l. Time from hospitalized in a post-anesthesia care unit (PACU) assessed at the Day 30 Visit
  - m. Time hospitalized in an intensive care unit (ICU), assessed at the Day 30 Visit
  - n. Length of surgery

- o. Total time in the operating room (OR)
- p. Occurrence of re-hospitalization, within 30 days of enrollment, including length of re-hospitalization (through 30 days post-enrollment)
- q. Occurrence of post-surgical major bleeding, as defined by International Society on Thrombosis and Hemostasis (ISTH) criteria, within 12 hours after the start of the initial surgery
- r. Occurrence of re-operations for bleeding, including for surgical wound hematomas, within 12 hours after the end of the initial surgery
- s. Change from baseline in tissue factor pathway inhibitor (TFPI) activity post-administration of andexanet
- t. Change from baseline in anti-IIa activity (only participants taking enoxaparin)

Removal of these endpoints also involves removal of applicable sections in the SAP (sections 5.5.1: Relationship Between Anti-fXa Activity and Hemostasis, 5.5.3: Reversal of Anticoagulant Effect – Thrombin Generation, 5.5.4: Blood Product Usage, 5.5.5: Intraoperative Blood Loss, 5.5.6: Transfusion Corrected Change in Hemoglobin, 5.5.57: Healthcare Encounter and Surgical Intervention, 5.5.8: Post-surgical Major Bleeding, 5.5.9: Tissue Factor Pathway Inhibitor (TFPI), and 5.5.10: Anti-IIa Activity.

- 8. Section 5.5.2: Anti-fXa Activity – Absolute and Percent Change from Baseline: 95% CIs will no longer be provided. Additionally, the tabulation of patients with percent reduction from baseline at time point >80% (and 95% CI) will also no longer be provided.
- 9. Section 5.6: Safety Analyses: We will no longer analyze the following:
  - a. Thrombotic Events (TEs) within 30 days of enrollment, including those suspected and confirmed by adjudication
  - b. Centrally adjudicated deaths within 30 days of enrollment, including all-cause mortality and cardiovascular mortality
  - c. Antibodies to FX, FXa, and andexanet

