##### **5.6.3.1. Hematology**

Hematology (hemoglobin, hematocrit, white blood cell [WBC] count, platelet count, WBC differential) assays are performed at the local laboratory and will be summarized using standardized units.

Descriptive statistics will be provided for the values at each time point as well as change from baseline at each time point. Tabulations will be performed for abnormal values relative to normal ranges at each visit, as well as shifts from baseline (low, normal, high) to each applicable time point/visit.

WBC differentials may be collected as absolute values and/or percentages. While only absolute values will be summarized, both absolute values and percentages will be presented in data listings. In cases where only the differential percentage is collected per local laboratory standards, the absolute value of the WBC type (eg, neutrophils) will be imputed for analysis as:

WBC type absolute value = WBC absolute count \* WBC type differential percentage

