### 6.7. Appendix 7: Protocol Schedule of Events

	Screening & Baseline		Treatment						Follow-up		
STUDY DAY:	1								2	3	30 or ET
TIME POINT AND WINDOW:			SURGERY			Post-Surgery					
			Bolus/Infusion Administration (can start up to 30 min before SoS)								
	-2 hours to -45 min Relative to SoS	-45 min to -30 min Relative to SoS	-30 min to -5 min Relative to SoS	End of Bolus ± 15 min	EoII -15 min	EoS [1] + 15 min [2]	EoS + 6 h ± 1 h	EoS + 12 h ± 1 h	EoS + 24 h ± 1 h	EoS + 48 h ± 1 h	+ 7 days
Obtain Consent	X										
Determine Eligibility	X										
Obtain Medical History	X										
Demographics	X										
Obtain Prior Medications and Time of Last Anticoagulant Dose or Plasma Level	X										
Obtain ASA Class			X								
Vital Signs (BP, HR, RR, temp)	X	X		X	X	X		X	X	X	X
Weight (actual reported/recent)	X										X
Physical Examination	X							X	X	X	X
Central Labs: Anti-fXa and anti-IIa Activity		X (pre-ADX)		X	X	X	X	X			
Central Labs: Thrombin Generation		X (pre-ADX)		X	X	X	X	X	X	X	
Central Labs: Antibodies to andexanet, HCPs, and FX/FXa (modified Bethesda); and NAb (andexanet)	X (pre-ADX)										X

	Screening & Baseline		Treatment					Follow-up			
STUDY DAY:	1							2	3	30 or ET	
TIME POINT AND WINDOW:				SURGERY		Post-Surgery					
	Bolus/Infusion Administration (can start up to 30 min before SoS)										
	-2 hours to -45 min Relative to SoS	-45 min to -30 min Relative to SoS	-30 min to -5 min Relative to SoS	End of Bolus ± 15 min	EoII -15 min	EoS [1] + 15 min [2]	EoS + 6 h ± 1 h	EoS + 12 h ± 1 h	EoS + 24 h ± 1 h	EoS + 48 h ± 1 h	+ 7 days
Central Labs: TFPI activity		X (pre-ADX)		X	X	X		X	X	X	X
Local Labs: PT-INR	X										
Local Labs: Chemistry and Pregnancy Test [3]	X										
Local Labs: CBC		X				X		X			X
Prepare Andexanet	X										
Administer Andexanet Bolus, Immediately Followed by an Infusion			X								
Assess Need for Extended Andexanet Infusion (if surgery ongoing)					X [4]						
Estimate Predicted Blood Loss			X [5]								
Surgical Intervention				SURGERY							
Record Blood Loss Post Surgery						X					
Record Investigator Assessment of Intraoperative Hemostasis						X					
Record Blood Products & Hemostatic Treatments [6]		X									

	Screening & Baseline		Treatment					Follow-up			
STUDY DAY:	1							2	3	30 or ET	
TIME POINT AND WINDOW:			SURGERY		Post-Surgery						
	Bolus/Infusion Administration (can start up to 30 min before SoS)										

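### Haematology abnormality and shift tables can miss a post-dose haemoglobin or platelet low, because they use only scheduled values and the last repeat; a worst-post-dose category would capture it

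*SAP*

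**What the plan says.** SAP Section 5.6.3 sets the rules for which laboratory values reach a table:

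- Scheduled values: "In general, only laboratory value collected at scheduled visit/time points will be summarized".
- Unscheduled values: "Laboratory value collected at unscheduled visits will be presented in data listings only".
- Repeats: "If an assessment is repeated for a given scheduled visit/time point, the last value will be used for summary purposes", with the safeguard "but all values will be presented in data listings".

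Section 5.6.3.1 applies these rules to the blood count, including haemoglobin and platelets: "Hematology (hemoglobin, hematocrit, white blood cell [WBC] count, platelet count, WBC differential) assays are performed at the local laboratory". Its safety tables are by visit or time point: "Tabulations will be performed for abnormal values relative to normal ranges at each visit, as well as shifts from baseline (low, normal, high"). It defines no lowest, highest or worst post-baseline category.

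In the Schedule of Events (Section 6.7), the row "Local Labs: CBC" is marked once before dosing and then at end of surgery (EoS), EoS + 12 h, and Day 30 or early termination. Section 5.1 says that no visit or time-point windows will be used.

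The addendum of 8 April 2022 leaves Section 5.6.3 unchanged. Among the exploratory analyses it removes (item 7h) is "Transfusion corrected change in hemoglobin from baseline to nadir within 12 hours after the end of surgery".

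**The concern.** A by-visit table answers what the values looked like at each planned time. A safety reader also asks whether a participant was ever abnormally low after dosing. Section 5.6.3.1 answers only the first question, and the filters in Section 5.6.3 can leave a real low out of the answer.

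The scheduled counts are sparse. After EoS + 12 h, the next count that can enter a table is at Day 30 or early termination. A count drawn in between, for example for suspected bleeding, goes to listings only, and without windows it cannot be assigned to a planned time point.

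For adverse events the SAP does take the worst case: Section 5.6.2.4 summarises the most severe occurrence per participant. The laboratory section has no counterpart. Once the addendum removes the haemoglobin nadir, the haematology tables are the only laboratory summary of post-dose haemoglobin. The abnormality and shift counts could then be too low in a study that examines safety around urgent surgery.

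**Working it through.** The SAP gives no figure for this rule, so there is nothing to reproduce. The check applies the rule to constructed cases.

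**Inputs from the SAP.** Only scheduled values are summarised, the last repeat is used, and unscheduled values are only listed (Section 5.6.3). Tables are by visit (Section 5.6.3.1). There are no windows (Section 5.1). Post-dose counts are at EoS, EoS + 12 h and Day 30 or early termination (Section 6.7). Ten participants were enrolled (addendum).

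**Assumed inputs.** The haemoglobin values are invented, in g/dL, with an assumed lower limit of normal of 12. A value is low if it is below the limit.

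**Method.** Under the SAP rule, a sequence is flagged if the last EoS value or the last 12 h value is low. Under a worst-value rule, it is flagged if the minimum of all post-dose values is low.

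| Sequence | EoS (in order) | Unscheduled | EoS + 12 h | SAP tables show a low | Worst value shows a low |
|---|---|---|---|---|---|
| A. Low, same-time-point repeat normal | 9, 12.5 | none | 12.5 | No | Yes |
| B. Low, repeat still low | 9, 9.4 | none | 12.5 | Yes | Yes |
| C. Low only at an unscheduled draw | 12.5 | 8 | 12.5 | No | Yes |
| D. Scheduled low, re-check entered as unscheduled | 9 | 12.5 | 12.5 | Yes | Yes |
| E. Scheduled low, next measured at 12 h | 9 | none | 12.5 | Yes | Yes |
| F. First value normal, repeat low | 12.5, 9 | none | 12.5 | Yes | Yes |

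The SAP rule shows the low in 4 of 6 sequences and the worst-value rule in 6 of 6. Any assumed limit above 9.4 and up to 12.5 gives the same counts. With a limit above 9 and up to 9.4, the repeat in B is no longer low, and the SAP rule shows 3 of 6. These counts describe the mechanism and do not estimate a frequency.

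**Length of the gap.** EoS + 12 h falls under Study Day 1 in the schedule. To the nominal last visit this is 30 − 1 = 29, so about 29 days without a scheduled count, and up to 7 more within that visit's window.

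**Size per affected participant.** 1/10 = 10 percentage points if all ten contribute a value, and more if fewer do. At the planned enrolment it would have been 1/100 = 1 point.

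**What else could recover the low.** The removed nadir analysis would have done so only in part. Under Sections 5.5 and 5.5.6 it used the Efficacy Set, covered only participants transfused during surgery, stopped at 12 hours after surgery, and did not include platelets. No other laboratory table uses a post-dose minimum for haemoglobin or platelets.

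**The case against.** The strongest reply is that scheduled-only, last-repeat handling is consistent with tables defined by visit and contradicts nothing in the SAP. This stands: the rule is acceptable for by-visit statistics, and the point is only what is missing beside it.

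Four stronger readings are tempting, and the document does not support them.

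- *Any low that was re-checked or treated disappears.* It does not. Sequences B, D, E and F keep it. In D, it is the re-check that goes to listings and the scheduled low that stays.
- *The rule always favours the recovered value.* The SAP does not say why counts are repeated, and in F the last value is the low one. The EoS sample is also to be taken within 15 minutes of the end of surgery (Section 6.7, footnote 2), so a later post-transfusion re-check may well be recorded as unscheduled, which leaves the scheduled low in the table.
- *No summary table would show the low.* Adverse event tables by system organ class and preferred term remain after the addendum and run through Day 30. A low reported as an event would be counted there, although that depends on its being reported.
- *The addendum took away an equivalent safeguard.* The nadir analysis was too narrow to be one.

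It might also be inferred that a participant who is dosed but not operated on has no scheduled post-dose count before Day 30. Section 3 does anticipate cancelled surgeries, but how they are followed is for the protocol, which is not at hand, so nothing is rested on this.

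Finally, all values are listed, and with 10 participants they can be read one by one. The study is single-arm with no hypothesis test, so no comparison is distorted. This limits the practical weight of the point but does not complete the tables.

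**Conclusion.** The point holds in a limited form. A post-dose haemoglobin or platelet low can be absent from the abnormal-value and shift tables if its same-time-point repeat is back in range, or if it was seen only at an unscheduled draw. After the addendum, no other laboratory summary recovers it. The listings do, and so do the adverse event tables if the low was reported as an event.

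The size is 10 percentage points per affected participant with ten contributing. The number affected cannot be estimated from the SAP. The conclusion rests on reading the blood-count row of the extracted schedule as described above, and on the words In general in Section 5.6.3 not covering an exception that the SAP leaves unstated.

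This is a cheap improvement of minor practical impact at 10 participants, and not an error in the by-visit rule.

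**What to change.** Leave the by-visit descriptive statistics and by-visit tables as they are. Add to Section 5.6.3.1, with a matching exception in Section 5.6.3, wording such as:

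> For each haematology parameter, abnormality and shift from baseline will also be tabulated for the worst post-dose value per participant, over all valid post-dose results through Day 30, including repeat and unscheduled tests. The worst value is the lowest for haemoglobin, haematocrit and platelet count. Only results that the laboratory has flagged as invalid are excluded.

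For white cell parameters, state the direction, for example lowest and highest tabulated separately.

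The cost is a few lines of SAP text and one extra category per parameter. The data are already required for the listings. The downside is that a worst value depends on how often a participant is tested, and sicker participants are likely to be tested more. The counts will look somewhat less favourable, so a footnote should say that unscheduled tests are included.
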